#### Attachments

[Back to Top](#)

**Study Population:** Describe the characteristics of the subject population, such as anticipated number, age range, gender, ethnic background and health status. Identify the criteria for inclusion and exclusion. Explain the rationale for the use of special classes such as fetuses, pregnant women, children, institutionalized, adults with impaired consent capacity, prisoners, economically or educationally disadvantaged persons or others who are likely to be vulnerable.

If women or minorities are included, please address how the inclusion of women and members of minority groups and their subpopulations will help you meet your scientific objectives. Exclusion of women or minorities requires clear and compelling rationale that shows inclusion is inappropriate with respect to the health of the subjects or that inclusion is inappropriate for the purpose of the study. Cost is not an acceptable reason for exclusion except when the study would duplicate data from other sources. Women of childbearing potential should not be excluded routinely from participation in clinical research.

Provide the following information:

- A description of the subject selection criteria and rationale for selection in terms of the scientific objectives and proposed study design;
- A compelling rationale for proposed exclusion of any sex/gender or racial/ethnic group;
- The proposed dates of enrollment (beginning and end);
- The proposed sample composition of subjects.

You may reference grant application/sponsor's relevant protocol pages and attach as an appendix using the below attachment button, however, a summary paragraph must be provided in the text box below.

The current study will use participants enrolled in the University of Kentucky Alzheimer's Center Longitudinal Cohort database sponsored by the University of Kentucky SBCoA. Individuals enrolled in this database undergo cognitive testing and are followed clinically by [name] at SBCoA. The database contains contact information, demographic information, results of cognitive tests, and caregiver information, along with other information as collected by SBCoA. Upon enrollment to the University of Kentucky Alzheimer's Center Longitudinal Cohort database, participants have agreed to be subjects in research and allow contact from SBCoA for invitations into additional research projects, such as the project explained in this IRB. Diagnosis of dementia creates significant cognitive impairment. All participants with these diagnoses will have cognitive impairment limiting their ability to independently provide informed consent. See section 6 regarding informed consent processes used to maximize participant understanding and participation.

Individuals with moderate to severe dementia with primary type as Alzheimer's disease and caregiver report of behavioral disturbance will be selected. Recruitment will occur continuously based on eligibility status and ADC cohort participation. This selective sampling approach will allow for greatest applicability and homogeneity for this study afforded by the cohort database at SBCoA.

In addition to individuals with dementia, this study will enroll caregivers of the subjects who have dementia. Individuals with dementia and their caregivers will create a participant dyad for data collection means. Enrollment of participant dyads is planned to occur upon IRB approval through May, 2021.

#### Inclusion Criteria:

Participants must meet all of the following inclusion criteria in order to participate in the study:

1. Men or women aged 21-90, inclusive.
2. Living at home in the community with one primary caregiver.
3. Diagnosis of Alzheimer's disease as primary dementia type of moderate to severe stages (confirmed by Clinical Dementia Rating Scale score of 1.5+)
4. Stable medical condition for one month prior to screening visit
5. Stable medications for 4 weeks prior to screening visit
6. If on psychotropic medication, they are at a point where dosage and treatment are stabilized for the duration of the study
7. Physically acceptable for this study as confirmed by medical history, physical exam, neurological exam and clinical tests completed by MD/APRN/PA
8. Functional sensory abilities with or without aids (hearing, vision, smell, touch, taste)
9. Caregiver report of challenges related to behaviors within 4 weeks of study enrollment
10. Caregiver willing to participant throughout duration of study
11. Caregiver access to and ability to use video technology (Zoom video call)
12. UKADC visit with medical provider within 24 months of study recruitment
13. Not actively participating in physical/occupational therapy for four weeks prior to or throughout duration of study

#### Exclusion Criteria:

1. Unstable medical conditions for three months prior to screening visit such as poorly controlled blood pressure, diabetes, or breathing problems...etc.
2. Wheelchair or bed bound.
3. Residence in skilled nursing facility or facility-based care.
4. Skin lesions or skin abnormalities throughout upper extremities.
5. Allergies related to lotion or fragrance.
6. Caregiver report of physically violent behaviors.
7. Initiation of antipsychotic medication within 6 weeks prior to screening or unstable use of such medications
8. Diagnosis of profound or total sensory altering disorders including macular degeneration, legal blindness, total deafness, severe peripheral neuropathy, anosmia.
9. Major depression in past 12 months (DSM-IV criteria), major mental illness such as schizophrenia, bipolar disorder, personality disorders, or recent (in past 12 months) alcohol or substance abuse.
10. Diagnosis or concern of epilepsy.
11. History of invasive cancer within the past two years.
12. Use of any investigational agents within 30 days prior to screening.
13. Major infection within eight weeks prior to the Baseline Visit.
14. Physically unacceptable for this study as confirmed by medical history, physical exam, neurological exam and clinical tests

Dates of Enrollment: Upon IRB approval-May, 2021

**Subject Recruitment Methods & Privacy:** Using active voice, describe plans for the identification and recruitment of subjects, including how the population will be identified, and how initial contact will be made with potential subjects by those having legitimate access to the subjects' identity and the subjects' information.

Describe the setting in which an individual will be interacting with an investigator or how and where members of the research team will meet potential participants. If applicable, describe proposed outreach programs for recruiting women, minorities, or disparate populations as participants in clinical research. Describe steps taken to minimize undue influence in recruiting potential participants.

Please note: Based upon both legal and ethical concerns, the UK IRB does not approve finder's fees or "cold call" procedures made by research staff unknown to the potential participant. The ORI/IRB does not control permission to any UK listserv, mass mailing list, etc. Investigators must secure prior approval for access and use from owners/managers.

For additional details, see topic "Recruitment of Subjects/Advertising" on ORI's [IRB Survival Handbook web page](#) and the [PI Guide to Identification and Recruitment of Human Subjects for Research](#).

The University of Kentucky SBCoA will assist in participant identification based on the participant database for the University of Kentucky Alzheimer's Center Longitudinal Cohort. Participants who have a Clinical Dementia Rating Score of 1.5 or above and reside in the community will be targeted for recruitment. Additional referrals will also be requested from SBCoA medical team staff. Of individuals identified, flyers will be mailed or emailed to the LAR on file with SBCoA and primary caregivers will be contacted via flyer and phone call from study personnel staffed at SBCoA. In addition, all patients with memory impairment of the Kentucky Neuroscience Institute (KNI) who are eligible for this study may be recruited for participation for this study. Recruitment from KNI will occur prior to informed consent including a review of medical records to identify additional subjects that are not in the recruitment database. This PHI information will be collected via AEHR UKHC (or EPIC). A waiver of informed consent is requested with this protocol. Information that will be collected prior to informed consent will include identifiable private health information including: Name, email address, phone number, DOB, address, medical history, diagnoses, medications, tests completed at SBCoA or KNI. Upon identification of eligible participants, the KNI medical team will determine patient interest to be contacted by study personnel and notify [name] (PI) to follow up with contact to potential participants and/or the study flyer will be mailed or emailed to eligible patients with request to contact study personnel if interested in study participation.

Explanation of no changes in care or participation at SBCoA and the University of Kentucky will be provided. All forms and data collected will be stored electronically on a secure web application, REDCap, sponsored by the Institute for Pharmaceutical Outcomes and Policy (IPOP) physically located in the new Biological and Pharmaceutical Complex building on University of Kentucky's campus. Video recordings will be captured through Zoom, in accordance with the University of Kentucky Telemedicine office and privacy standards. All material will be stored for six years, at which time the content will be deleted and destroyed. Participant and caregiver confidentiality will be maintained through use of pseudonyms and removal of identifying information. The results of this study will be published. In accordance with UK Alzheimer Disease Center data sharing policies, access to the de-identified, raw data collected will be restricted up to a period of 1 year after final data is collected and the primary manuscript is published. After such time, the full dataset will be made available for independent analysis and publication without restriction.

[Back to Top](#)

**Advertising:** Specify if any advertising will be performed. If yes, please see ["IRB Application Instructions - Advertisements"](#) for instructions on attaching copies of the information to be used in flyers or advertisements. Advertisements must be reviewed and approved by the IRB prior to use. For additional details, see topic "Recruitment of Subjects/Advertising" on ORI's [IRB Survival Handbook](#) web page for the [PI Guide to Identification and Recruitment of Human Subjects for Research](#) [D7.0000] document [\[PDF\]](#). If you will be recruiting subjects via advertising at non-UK owned or operated sites, you should include a copy of written permission from that site to place the advertisement in their facilities.

Note: Print and media advertisements that will be presented to the public also require review by UK Public Relations (PR) to ensure compliance with UK graphic standards, and equal opportunity language. See [Advertising Instructions](#) for PR contacts. [\(i\)](#)

Advertisement with Flyer approved, Stamped approval attached.

Attach Type	File Name
Advertising	Rhodus_Flyer MP edit STAMPED.pdf

**Informed Consent Process:** Using active voice, describe the consent/assent procedures to be followed, the circumstances in which consent will be sought and obtained, the timing of obtaining informed consent, whether there is any waiting period between informing the prospective subject and obtaining consent, who will seek consent, steps taken to minimize the possibility of coercion or undue influence, the method used for documenting consent, and if applicable who is authorized to provide permission or consent on behalf of the subject. Note: all individuals authorized to obtain informed consent should be designated as such in the E-IRB "Study Personnel" section of this application.

Describe provisions for obtaining consent/assent among any relevant special populations such as children (see Children in Research Policy [[PDF](#)] for guidance), prisoners (see Summary of Prisoner Regulations [[PDF](#)] for guidance), and persons with impaired decisional capacity (see Impaired Consent Capacity Policy [[PDF](#)] for guidance). Describe, if applicable, use of specific instruments or techniques to assess and confirm potential subjects' understanding of the nature of the elements of informed consent and/or a description of other written materials that will be provided to participants or legally authorized representatives. If you have a script, please prepare it using the informed consent template as a guide, and submit it on a separate page.

#### *Informed Consent for Research Involving Emancipated Individuals*

If you plan to enroll some or all prospective subjects as emancipated, consult with UK legal counsel **when preparing the IRB application and prior to submitting the application to the IRB**. Include legal counsel's recommendations (legal counsel's recommendations may be attached in the E-IRB "Additional Information" section as a separate document, if necessary). For a complete definition of emancipated minors, see the section on *Emancipated Individuals* in the Informed Consent SOP [[PDF](#)].

#### *Informed Consent for Research Involving Non-English Speaking Subjects*

If you are recruiting non-English speaking subjects, the method by which consent is obtained should be in language in which the subject is proficient. Describe the process for obtaining informed consent from prospective subjects in their respective language (or the legally authorized representative's respective language). In order to ensure that individuals are appropriately informed about the study when English is their second-language, describe a plan for evaluating the level of English comprehension, and the threshold for providing a translation, or explain why an evaluation would not be necessary. For additional information on inclusion of non-English speaking subjects, or subjects from a foreign culture, see [IRB Application Instructions for Recruiting Non-English Speaking Participants or Participants from a Foreign Culture](#).

#### *Research Repositories*

If the purpose of this submission is to establish a research repository describe the informed consent process. For guidance regarding consent issues, process approaches, and sample language see the Sample Repository/Registry/Bank Consent Template [[PDF](#)]

A waiver of informed consent is included within this proposal, along with access to HIPAA information prior to obtaining informed consent for participation. PHI from KNI medical records will be accessed for recruitment purposes through the AEHR UKHC system. PHI and identifying information will be sought from SBCoA participant charts. PHI accessed will include: Name, DOB, email address, phone number, address, medical history, diagnoses, medications, tests completed, and/or visit notes at Sanders-Brown Center on Aging or the Kentucky Neuroscience Institute.

Given the nature of cognitive impairment associated dementia (see Form T), upmost precaution and protection will be included in the informed consent process. The intent of this study is to conduct research with severely cognitively impaired participant whom may also have communication deficits. Participants have associated dependency on caregivers/LAR for decision making, safety, and activities and/or instrumental activities of daily living. Explanation of the study objectives, informed consent process and confidentiality will be explained to the individuals with cognitive impairment and their caregiver/LAR. If the dyad is willing to participate, informed consent will be sought by:

During pre-screening, it will be determined if the patient has a legally authorized representative/advocate. If so, the consent will be sent to and signed by this person (LAR) and assent will be obtained from the patient. If the patient does not have legally authorized representative and appears oriented (to time, place, person) and is able to verbalize understanding of the study expectations and risks, informed consent will be signed by the patient with patient advocate present.

Informed consent will be collected via several ways. The electronic or hard copy IRB-Stamped informed consents will be emailed/mailed to the person with dementia's legally authorized representative (LAR) or the patient with dementia and their care advocate if LAR is not established (patient consent form), and their identified caregiver (caregiver consent form). An electronic form e-Consent will be emailed to both individuals (LAR and Caregiver) and required for signature using REDCap technology. This form will be signed prior to the screening visit, or after thorough review during the screening visit, along with assent obtained from the person with dementia. The assent form will be discussed and used with the patient via Zoom video conferencing during screening visit. Verbal confirmation of understanding and willingness to participant will be sought. If they are unable to provide verbal communication, non-verbal cues such as head nodding (described in Form T) will be collected. If non-verbal cues are unable to be collected, consent will be deferred entirely to the LAR.

A copy of the consent form will be emailed or mailed to the participants prior to Visit 1. LAR's, participants with dementia, and caregivers will be advised that participation is strictly voluntary, and they can withdraw from the study at any time. Participants will be assured that participation or nonparticipation of this study will have no direct effect on enrollment or participation of SBCoA program and healthcare services.

A waiver of documentation of informed consent will be used for administration of the Situational Assessment of Activity and Function (SAAF) survey. A link will be emailed to caregiver participants with a cover letter explaining the assessment. Participants are not required or obligated to respond to the email or survey and all responses will be deidentified. Completion of the assessment and feedback via email to the study PI regarding participants' experience with the assessment will indicate implied consent.

**Research Procedures:** Describe the research procedures that will be followed. Identify all procedures that will be carried out with each group of subjects. Differentiate between procedures that involve standard/routine clinical care and those that will be performed specifically for this research project.

For this study, the following step-by-step sequence will be used. Recruitment will occur via discussion with SBCOA medical team (MD/APRN/PA) and [name] of appropriate referrals of heightened cognitive impairment with behavioral disturbance. Additionally, SBCOA records will be reviewed for all eligible cohort participants. These participants will be contacted via SBCOA recruitment team with calling, mailing, and/or emailing eligible participants with an invitation to participate in the current study. Following agreement to participate, SBCoA staff and researcher will coordinate with the participant a date and time for Visit 1 to be completed via a virtual telemedicine platform. All visits within this study will be scheduled at times convenient for the participants using telemedicine Zoom video conferencing. Videos will be recorded and saved on private and secure server hosted by Sanders-Brown Center on Aging Data Management Team.

During the screening visit, a research assistant or PI will review and obtain consent as described above, talk with the LAR and caregiver to determine eligibility status, and record medications. The PI will complete a UKADC or KNI chart review of medical conditions, medications, and symptoms from the prior 24 months if available. Records will be assessed for most recent vital signs (systolic and diastolic blood pressure, pulse, temperature, and respiration), known allergens, chronic medical conditions, recent medical changes, and medications. The PI (OT) or UKADC medical staff (MD/APRN/PA) will conduct a physical and neurological examine via Telemedicine. The physical examination will include skin, head/ears/eyes/nose/throat (HEENT), oral/teeth/gums (history of dental problems/dentures), sensory function, gait/walking ability, and musculoskeletal range of motion of upper extremities. All complete physical and neurological examination data will be entered on the appropriate CRF. Neurological assessment will include of cranial nerves, strength, coordination, symmetry of movements, and movement speed. Verbal assessment of patients' sensory function (including hypersensitivity) with caregiver will occur at the screening. Significant abnormalities consistent with disease processes will be documented.

Once eligibility is confirmed, the research assistant will email a REDCap link to the caregiver for the Zarit Caregiver Burden and the Adult Sensory Profile, Actigraph and charger, and a copy of consent forms to the participant's caregiver. The PI will complete the COPM on visit 1, and provide caregiver and participant with Actigraph wear and care instructions. The VABS will be emailed to the caregiver via a confidential link through Pearson Publishing.

Subjects will be randomized to treatment arms by the statistical team. Participants will be randomized into one of the three groups: control, standard environmental design protocol, individualized environmental design protocol. Recruitment will be ongoing until all groups have 10 participants. In the event of drop out or early termination (causes will be recorded), researchers will recruit for replacement participants so that the study is completed with 30 entire study duration cases.

Visit 2 will consist of baseline assessment. A research assistant or the PI will complete the MOCA, with the participant with dementia. The caregiver will complete the NPI. Following Visit 2, an occupational therapist will be provided results of the COPM and ASP for participants of the individualized treatment arm. A sensory protocol will be developed based on assessment results following predetermined guidelines. All intervention materials for all study participants will be mailed to caregivers within 4 days of Visit 2. Upon receipt of intervention supplies, caregivers will contact the PI or occupational therapist for study initiation. Visit 3 will provide caregiver training for intervention use and initiation of Actigraph use. Adverse events since Visit 2 will be recorded. Visit 3 marks day 1 of intervention implementation. Participants will mail Actigraph back to UKADC in provided pre-paid envelop following week one of intervention.

Visits 4-8 will be scheduled at the end of each week following Visit 3. The PI, occupational therapist, or research assistant will record concurrent medication, and adverse events. With the caregiver, the interviewer will review behaviors observed by the caregiver, the behavior journal, compliance and acceptance of the intervention by the caregiver and the person with dementia. Actigraphs will be mailed from UKADC to participants, and patient will be asked to wear actigraph for last week of intervention window.

Visit 9 will conclude the intervention window at the end of week 4. The PI, occupational therapist, research assistant will record adverse events, concurrent medication, Actigraph, and weekly behavior journals/compliance. The research assistant will conduct the NPI, COPM, VABS with the caregiver and the MOCA with the person with dementia. A member of the SBCoA medical team will conduct a physical and neurological exam. Due to the length of assessments within Visit 7, this session may be split and completed in more than one Zoom conference. The Zarit Caregiver Burden Scale will be emailed or mailed to the caregiver with prepaid envelop for return.

A four-week follow up will be conducted at Visit 10 whereby the research assistant will conduct the NPI, COPM, VABS with the caregiver, and the MOCA with the person with dementia. A member of the SBCoA medical team will conduct a physical and neurological exam. The Zarit Caregiver Burden Scale will be emailed or mailed to the caregiver with prepaid envelop for return.

Schedule of events can be found in attached detailed protocol.

A list of potential items sent in sensory kit is attached here.

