## Statistical Analysis

Participants' characteristics were compared among the three arms using analysis of variance (ANOVA) for continuous measures and chi-square tests or Fisher's exact for categorical measures. The analysis of the primary endpoint used a chi-square test to compare the proportion of participants completing at least 75% of the video sessions among the study arms. The analysis of all secondary and exploratory endpoints relied on a modified intention-to-treat (mITT) strategy in which participants were included in the analysis only if the dyad completed at least one video session. For those endpoints, the main analysis tool was ANCOVA in which the mean value of an endpoint at the end of the intervention period was adjusted for baseline and then compared among the study arms. Sensitivity analyses were conducted in which multiple imputation was used for missing responses at the end of the intervention period (regressed on baseline) and in which the list of covariates included age of the person with AD at baseline and gender of the caregiver when appropriate. These sensitivity analyses did not change any of the conclusions drawn from the reported ANCOVA in Table 3 and are not reported here. A further sensitivity analysis included the measurements made at the four-week follow-up and relied on ANCOVA to compare the profile of responses at the end of the intervention and at the four-week follow-up each adjusted for baseline. This analysis did not change the conclusions drawn from Table 3 and is not reported here. All analyses were done using PC-SAS, Version 9.4.

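### The procedure sequence places randomisation before the Visit 2 baseline NPI and MoCA, with no stated release time for the arm and no named blinded party

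*Combined protocol and SAP*

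**What the plan says.** Research Procedures opens with "For this study, the following step-by-step sequence will be used". The steps then run in this order:

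- **After eligibility and at Visit 1.** "Once eligibility is confirmed, the research assistant will email a REDCap link to the caregiver for the Zarit Caregiver Burden and the Adult Sensory Profile". "The PI will complete the COPM on visit 1". "The VABS will be emailed to the caregiver via a confidential link through Pearson Publishing". No return deadline is given for the emailed forms.
- **Randomisation.** "Subjects will be randomized to treatment arms by the statistical team". The same paragraph covers recruiting until each group has 10 and replacing drop-outs so that 30 cases complete the study.
- **Visit 2.** "Visit 2 will consist of baseline assessment. A research assistant or the PI will complete the MOCA, with the participant with dementia". The caregiver completes the NPI.
- **After Visit 2.** An occupational therapist receives the COPM and Adult Sensory Profile results for the individualized arm. Materials for all arms are mailed within 4 days of Visit 2.

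The study design text calls the trial single-blind but does not name the blinded party. Research Procedures refers to a schedule of events in an attached detailed protocol, which is not among the documents available here.

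Two analyses use the baselines. Data Analysis compares mean change from baseline by ANOVA and names VABS and NPI among its measures. Statistical Analysis uses ANCOVA for all secondary and exploratory endpoints, in which "the mean value of an endpoint at the end of the intervention period was adjusted for baseline".

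**The concern.** Randomisation protects a baseline-adjusted comparison as long as the measured baseline is unaffected by the allocation. The surest way to secure that is to finish the baseline before anyone can know the arm. Here the listed order puts allocation first, and no available text fills the gap with concealment, a release time or a locked baseline.

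Both Visit 2 measures depend on people who are not clearly blinded. The NPI is rated by the caregiver, who will deliver the intervention. The MoCA may be given by the principal investigator, who is one of the two contacts for starting the intervention. A caregiver who knew the arm might rate behaviour as worse or better before treatment begins. That shift would enter the baseline covariate and reappear, with opposite sign, in the adjusted treatment difference.

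A second risk does not depend on anyone knowing the arm. A dyad randomised and then lost before Visit 2 belongs to an arm but has no baseline NPI or MoCA.

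**Working it through.** **No figure in the plan to reproduce.** The documents give no baseline-to-outcome slope, no SD and no effect size. The only stated number is 3 arms × 10 = 30. The sizes below are illustrations under assumed values.

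**Step 1: which baselines are exposed.**

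| Measure | Placement relative to the randomisation paragraph | Exposure |
|---|---|---|
| COPM | Completed at Visit 1, before it | Not exposed by the listed order |
| Zarit, VABS | Sent out before it, no return deadline | Possible if returned late |
| NPI, MoCA | Visit 2, after it | Exposed by the listed order |
| Primary endpoint in Statistical Analysis (75% of video sessions) | Uses no baseline | None |

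**Step 2: bias formula.** Suppose there is no true effect, outcome = slope × true baseline + error, and the measured baseline is shifted by *s* SD in one arm.

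- ANCOVA: the unadjusted outcome difference averages 0 and the adjustment subtracts slope × *s*, so bias = −slope × *s*.
- Change score: bias = 0 − *s* = −*s*.

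**Step 3: numbers (absolute size, assumed inputs).**

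- Slope 0.5, shift 0.2: 0.5 × 0.2 = 0.10 SD.
- Slope 0.7, shift 0.5: 0.7 × 0.5 = 0.35 SD.
- Wider range, slope 0.3 to 0.8: 0.3 × 0.2 = 0.06 SD up to 0.8 × 0.5 = 0.40 SD.
- Change-score ANOVA for the same shifts: 0.20 to 0.50 SD.

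**Step 4: simulation check** (20,000 runs, two arms of 10, no true effect, two-sided 5% assumed).

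| Shift (SD) | Slope | Mean ANCOVA bias (SD) | False-positive rate |
|---|---|---|---|
| 0 | 0.5 | 0.00 | 4.9% |
| 0.3 | 0.5 | −0.15 | 6.3% |
| 0.5 | 0.5 | −0.25 | 8.9% |
| 0.5 | 0.8 | −0.40 | 27.0% |

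The simulated biases match the formula. With no shift, there is no bias. For scale, 10 per arm gives about 80% power (79.8%, normal approximation, no baseline adjustment) only for a difference near 1.25 SD.

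**Step 5: loss before Visit 2.** One such dyad is 1/10 = 10% of an arm before replacement. The multiple imputation in Statistical Analysis fills in end-of-intervention responses by regression on baseline, so it has nothing to regress on for a dyad without one. Replacement restores the count of 30, but the replacement is a different dyad and does not restore the comparison as randomised.

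**Step 6: is early allocation needed?** The first described use of the arm is the hand-over to the occupational therapist after Visit 2. The first described event that would reveal it to caregivers is the mailing. No stated step needs the arm earlier.

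**The case against.** The strongest reply is that the timing is inferred. The randomisation sentence gives no visit, day or trigger, and its paragraph includes recruitment totals and replacement, which are not steps between two visits. The section is not strictly chronological elsewhere either: it gives Actigraph instructions at Visit 1 and starts Actigraph use at Visit 3, although the device description asks for a baseline week, and its Visit 9 text refers to Visit 7. Allocation is by the statistical team, which could hold the arm until after Visit 2, and the unavailable schedule may settle the matter.

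Much of this stands, and it rules out several stronger readings that a reader might infer:

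- That baseline was scored with the arm known. No text says so.
- That every ANCOVA covariate is compromised. The clear exposure is NPI and MoCA.
- That ANCOVA is invalid unless baseline precedes randomisation. A baseline taken after randomisation but before disclosure or treatment is unaffected by the arm.
- That the principal investigator trains the caregivers. No Visit 3 trainer is named.
- That each early loss permanently shrinks an arm by 10%. Drop-outs are replaced.

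It is also fair that the study calls itself not fully powered and its behaviour results exploratory, and that replacement and the one-session rule for the analysis set create selection whatever the timing of Visit 2.

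What does not fall is the order itself. The section announces a sequence, that sequence puts randomisation before Visit 2, no available text puts it later, and no safeguard is described for the interval.

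**Conclusion.** The point holds in a limited form. Followed as written, the sequence allows the arm to be known when baseline NPI and MoCA are recorded, and allows dyads to be lost after randomisation with no baseline on those measures. Whether either happened cannot be told from the documents.

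If the arm were known, the ANCOVA bias would be 0.10 to 0.35 SD for a shift of 0.2 to 0.5 SD in one arm and a slope of 0.5 to 0.7. The change-score comparison, which names NPI but not MoCA, would be biased by the full shift. Both slope and shift are assumptions, and the direction of any shift is unknown. The primary endpoint and COPM are not affected by this ordering; Zarit and VABS are affected only if returned after the arm is known. The point merits a change because the remedy is nearly free, not because bias has been shown.

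**What to change.** Move the randomisation paragraph to follow Visit 2. State that the statistical team randomises, or at least releases the arm, only when all Visit 1 and Visit 2 baseline measures, including the returned Zarit, VABS and Adult Sensory Profile forms, are entered and locked. Name the blinded party. Say how a dyad without baseline NPI or MoCA is handled in the analysis.

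This needs no extra visit or staff and changes no sample-size figure. The cost is a slightly tighter window for preparing individualized kits within the 4 days after Visit 2.

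If enrolment is already complete, as the closed status and the past tense of Statistical Analysis suggest, report instead the randomisation dates relative to Visit 2, who knew the arm at that visit, and the number of dyads by arm lost in between.
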